5.2 Contraception Recommendations

Contraception Requirements for Females

Subjects must follow the following contraceptive guidelines as specified:

• Females, Non-Childbearing Potential

Females do not need to use birth control during or following study drug treatment if considered of non-childbearing potential due to meeting any of the following criteria:

- Postmenopausal, age > 55 years with no menses for 12 or more months without an alternative medical cause.
- Postmenopausal, age ≤ 55 years with no menses for 12 or more months without an alternative medical cause AND a follicle stimulating hormone (FSH) level > 40 IU/L.
- Permanently surgically sterile (bilateral oophorectomy, bilateral salpingectomy, or hysterectomy).

Females, of Childbearing Potential

- Females of childbearing potential must avoid pregnancy while taking study drug and for at least 30 days after the last dose of study drug. Females must commit to one of the following methods of highly effective birth control:
 - Combined (estrogen- and progestogen-containing) hormonal birth control (oral, intravaginal, transdermal, injectable) associated with inhibition of ovulation initiated at least 30 days prior to study Baseline Day 1.
 - Progestogen-only hormonal birth control (oral, injectable, implantable) associated with inhibition of ovulation initiated at least 30 days prior to study Baseline Day 1.
 - Bilateral tubal occlusion/ligation (can be via hysteroscopy, provided a hysterosalpingogram confirms success of the procedure) (For Japan: only bilateral tubal ligation).
 - Intrauterine device.
 - Intrauterine hormone-releasing system.
 - Vasectomized sexual partner (the partner has received medical confirmation of the surgical success of the vasectomy and is the sole sexual partner of the trial subject).
 - Practice true abstinence (unless not acceptable per local practices), defined as: refraining from heterosexual intercourse when this is in line with the preferred and usual lifestyle of the subject (periodic abstinence [e.g., calendar, ovulation, symptothermal, post-ovulation methods] and withdrawal are not acceptable).
- If required per local practices, females of childbearing potential must commit to using 2 methods of contraception (either 2 highly effective methods or 1 highly effective method combined with 1 effective method). Effective methods of birth control are the following:
 - Progestogen-only oral hormonal contraception, where inhibition of ovulation is not the primary mode of action, initiated at least 30 days prior to Study Day 1.
 - Male or female condom with or without spermicide.
 - Cap, diaphragm, or sponge with spermicide.
 - A combination of male condom with a cap, diaphragm, or sponge with spermicide (double barrier method).

Contraception recommendations related to use of concomitant therapies prescribed per standard of care should be based on the local label.

5.3 Prohibited Medications and Therapy

Background Therapies

The following therapies are prohibited until after Week 16 assessments unless otherwise specified:

- 1. Throughout the study, any other systemic therapy that can also be used to treat HS, including but not limited to intramuscular or intravenous corticosteroids, oral corticosteroids equivalent to > 10 mg/day of prednisone, methotrexate (> 25 mg/week), cyclosporine, mycophenolate mofetil, azathioprine, intramuscular gamma-globulin.
- 2. Apremilast, hormonal therapy (except for contraception), metformin (except for continuous treatment of preexisting diabetes), zinc gluconate, colchicine, retinoids, acitretin/etretinate, and fumaric acid esters, methotrexate, and oral corticosteroids are prohibited until after Week 16 assessments.
- 3. New topical therapies used to treat HS (other than protocol-allowed antiseptic) or changes in the concentration/frequency of current topical therapies used to treat HS (including but not limited to exfoliants, e.g., resorcinol).
- 4. Deroofing or skin-tissue-saving excision with electrosurgical peeling (STEEP), laser therapy, intense pulse light, local/wide/radical excision, incision and/or draining of lesions, or intralesional corticosteroid injections.
- 5. Concomitant use of antibiotics (topical or systemic) is not permitted for the treatment of HS or other chronic inflammatory disorders.
- 6. Use of any treatments for HS-related pain, other than ibuprofen or acetaminophen (paracetamol), including but not limited to opioids, antiepileptics (e.g., gabapentin), tricyclics (e.g., nortriptyline), or selective serotonin norepinephrine reuptake inhibitors (e.g., duloxetine, venlafaxine). For non-HS-related pain, all other non-opioid analgesics are allowed at the recommended or prescribed dose per local label. Use of opioid analgesics for HS-related or non-HS related pain is prohibited until after Week 16 assessments.
 - Subjects who are on a documented stable dose and dosing regimen of non-opioid analgesic treatment for at least 14 days prior to the Baseline visit are not permitted to adjust their regimen at least until after the Week 16 assessment. Note: For HS-related pain, analgesic therapy is limited to ibuprofen (as per local labeling, but not exceeding a dose of 800 mg orally every 6 hours and 3.2 g orally every 24 hours) AND/OR acetaminophen (paracetamol) as per local labeling.
- 7. Over-the-counter topical antiseptic washes (other than those allowed as per the concomitant therapy section), creams, ointments, gels, and liquids containing antibacterial agents to treat HS, other than those allowed as per concomitant therapy section.
- 8. Phototherapy treatment (ultraviolet B or ultraviolet A phototherapy, including psoralen and ultraviolet A), tanning booth, or extended sun exposure.
- 9. Medicinal and recreational cannabis.

Biologic Therapies

Subjects must have discontinued biologic therapies at least 3 months or 5 half-lives (whichever is longer) prior to Baseline or with specified washout periods as detailed in Section 5.1. No minimum washout prior to Baseline is required for a biologic therapy if an undetectable drug level measured by a commercially available assay is documented.

Therapies including but not limited to the following biologic therapies are prohibited medications during the study (throughout Period 1 and Period 2):

- Abatacept
- Adalimumab
- Anakinra
- Belimumab
- Certolizumab
- Dupilumab
- Etanercept
- Golimumab
- Infliximab
- Ixekizumab
- Natalizumab
- Rituximab
- Secukinumab
- Tocilizumab
- Ustekinumab
- Vedolizumab
- Guselkumab
- Risankizumab

Strong CYP3A Inhibitors or Inducers

Systemic use of known strong CYP3A inhibitors (includes over-the-counter or prescription medicines, vitamins and/or herbal supplements) is not permitted from Screening through the end of study drug administration and use of strong CYP3A inducers is not permitted from 30 days prior to study drug administration through the end of study drug administration. Table 1 includes examples of commonly used strong CYP3A inhibitors and inducers. In addition, herbal therapies and other traditional medicines with unknown effects on CYP3A are not permitted from Screening through the end of study drug administration.

Table 1. Examples of Commonly Used Strong CYP3A Inhibitors and Inducers

Strong CYP3A Inhibitors	Strong CYP3A Inducers
Boceprevir	Avasimibe
Cobicistat	Carbamazepine
Clarithromycin	Phenytoin
Conivaptan	Rifampin (rifampicin)
Grapefruit (fruit or juice)	Rifapentine
Indinavir	St. John's Wort
Itraconazole	
Ketoconazole	
Lopinavir/Ritonavir	
Mibefradi	
Nefazodone	
Nelfinavir	
Posaconazole	
Ritonavir	
Saquinavir	
Telaprevir	
Telithromycin	
Troleandomycin	
Voriconazole	

Investigational Drugs or Therapies

Subjects who have been treated with any investigational drug within 30 days or 5 half-lives of the drug (whichever is longer) prior to the first dose of study drug are excluded from participation in this study. Investigational drugs are also prohibited during the study.

Vaccines

If the subject and investigator choose to receive/administer live vaccines, these vaccinations must be completed (per local label) at least 28 days (or longer if required locally) before first dose of study drug. Live vaccinations are prohibited during study participation including at least 30 days (or longer if required locally) after the last dose of study drug.

If the live herpes zoster vaccine is to be administered and there is no known history of primary varicella (chicken pox), preexisting immunity to varicella should be confirmed with antibody testing at or prior to Screening and prior to administration of the herpes zoster vaccine. If screening varicella antibody testing is negative, the live herpes zoster vaccine should not be administered.

Examples of live vaccines include, but are not limited to, the following:

- Monovalent live influenza A (H1N1) (intranasal);
- Seasonal trivalent live influenza (intranasal);
- Zostavax (herpes zoster, live attenuated);
- Rotavirus;

- Varicella (chicken pox);
- Measles-mumps-rubella or measles-mumps-rubella-varicella;
- Oral polio vaccine;
- Smallpox;
- Yellow fever;
- Bacille Calmette-Guérin;
- Typhoid (oral).

Administration of inactivated (non-live) vaccines is permitted prior to or during the study according to local practice guidelines. Examples of common vaccines that are inactivated, toxoid or biosynthetic include, but are not limited to, injectable influenza vaccine, pneumococcal, Shingrix (zoster vaccine, recombinant, adjuvanted), and pertussis (Tdap) vaccines.

Other Medications Prohibited During the Study

JAK inhibitors (e.g., upadacitinib [Rinvoq®], tofacitinib [Xeljanz®], ruxolitinib [Jakafi®], baricitinib [Olumiant®], peficitinib [Smyraf®], abrocitinib [PF-04965842], and filgotinib).

5.4 Prior and Concomitant Therapy

Any medication or vaccine (including over-the-counter or prescription medicines, vitamins and/or herbal supplements) that the subject is receiving at the time of screening, and/or receives during the study, must be recorded along with the reason for use, date(s) of administration including start and end dates, and dosage information including dose, route and frequency on the appropriate electronic case report form (eCRF). Also, medications taken for HS since date of diagnosis (based on subject recollection and available medical records) should be entered into the appropriate eCRF inclusive of the dates of first and last dose, maximum dosage taken, route of administration.

Any questions regarding concomitant or prior therapy should be raised to the AbbVie Therapeutic Area Medical Director (TA MD)/AbbVie emergency contact. Information regarding potential drug interactions with upadacitinib can be located in the upadacitinib Investigator's Brochure.

Allowed Therapies

Antibiotics

Concomitant use of antibiotics is allowed for the treatment of acute infections during the study. Use of topical or systemic antibiotics to treat HS or other chronic inflammatory disorders is prohibited up to Week 16. After Week 16, concomitant use of any antibiotics for any indication, including HS, is permitted.

Dosing and/or frequency need to be reported in the eCRF documentation; "as needed" (PRN) use is not permitted.

Antiseptic Wash

Subjects are required to use a daily antiseptic wash on their HS lesions for the duration of the study.

Allowable antiseptic washes are limited to: chlorhexidine gluconate, benzoyl peroxide, benzalkonium chloride, or dilute bleach in bathwater.

Wound Care

Use of wound care dressings on HS wounds is allowed. Recommended options include alginates, hydrocolloids, and hydrogels.

Lesion Intervention

Deroofing or STEEP, laser therapy, intense pulse light, local/wide/radical excision, incision and/or draining of lesions, and intralesional injections are allowed after Week 16 assessments. Refer to Section 6.2 for study drug interruption guidelines for elective and emergency surgeries.

Analgesic therapy

If a subject experiences pain (HS- related or non-HS-related) after Baseline, they may initiate analgesic treatment. For HS-related pain, analgesic therapy is limited to the following until after the Week 16 assessments:

- ibuprofen as per local labeling, but not exceeding a dose of 800 mg orally every 6 hours and 3.2 grams orally every 24 hours, AND/OR
- acetaminophen (paracetamol) as per local labeling

For non-HS-related pain, all other non-opioid analgesics are allowed at the recommended or prescribed dose.

Use of opioid analgesics for HS-related or non-HS related pain is prohibited until after Week 16 assessments.

Subjects will complete a daily diary of their analgesic use. Subjects will be required to record their analgesic use daily through Week 16. Any changes in dosing and/or frequency need to be reported in the daily dairy; documentation of only PRN use is not permitted.

Subjects who are on a documented stable dose and dosing regimen of non-opioid analgesic treatment for at least 14 days prior to the Baseline visit may not adjust their regimen until after Week 16 assessments.

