Available treatment options for patients with HS include medical treatments such as topical non-antibiotics (e.g., exfoliants and peels), topical antibiotics (e.g., clindamycin), systemic antibiotics (e.g., clindamycin, tetracycline, rifampicin), anti-inflammatory therapies (e.g., corticosteroids, dapsone, ciclosporin A), hormones (e.g., antiandrogens and estrogens), retinoids (e.g., isotretinoin, acitretin), biologics (e.g., adalimumab, infliximab), analgesics (e.g., nonsteroidal anti-inflammatory drugs [NSAIDs], opioids), and surgical treatments (e.g., deroofing, excision, laser). However, with the exception of adalimumab, most of those treatments have not been adequately studied in patients with HS or do not appear to be very effective through the course of the disease. The only approved treatment option for patients with moderate to severe HS is adalimumab (Humira®), a tumor necrosis factor (TNF)- α inhibitor. The results from Phase 3 studies with adalimumab, PIONEER I and II, showed approximately 42% and 59% of subjects achieved Hidradenitis Suppurative Clinical Response (HiSCR) at Week 12, respectively, versus 26% and 28% in placebo. HiSCR is defined as a reduction of at least 50% of total abscess and inflammatory nodule (AN) count, without an increase in abscesses or draining fistula count relative to Baseline. Additional treatment options are needed for those patients who fail to achieve adequate efficacy.

The Janus kinases (JAKs) are a family of intracellular tyrosine kinases that function as dimers in the signaling process of many cytokine receptors. The JAK family is composed of 4 members: JAK1, 2, 3, and tyrosine kinase 2 (Tyk2). These cytoplasmic tyrosine kinases act in tandem to activate the signal transducer and activator of transcription (STAT) that transduce cytokine-mediated signals, and are associated with multiple membrane cytokine receptors such as common gamma-chain receptors and the glycoprotein 130 trans-membrane proteins. The JAKs play a critical role in both innate and adaptive immunity, making them attractive targets for the treatment of inflammatory diseases.

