- 21. Subject must have no systemic use of known strong cytochrome P450 3A (CYP3A) inhibitors from Screening through the end of study drug administration or strong CYP3A inducers 30 days prior to study drug administration through the end of study drug administration (refer to Table 1 for examples of commonly used strong CYP3A inhibitors and inducers). Subjects may not use herbal therapies or other traditional medicines with unknown effects on CYP3A from Screening through the end of study drug administration.
- 22. Subject must not have received a live vaccine within 28 days (or longer if required locally) prior to the first dose of study drug, or have expected need of live vaccination during study participation including at least 30 days (or longer if required locally) after the last dose of study drug.
- 23. Subject must not have a history of an allergic reaction or significant sensitivity to constituents of the study drug (and its excipients) and/or other products in the same class.
- 24. Subjects who have had prior exposure to immunomodulatory biologic therapies for any indication, including but not limited to anti-TNF therapy and anti-IL-1 (e.g., anakinra, canakinumab) therapy must have discontinued the biologic therapies prior to the first dose of study drug. Subjects who need to discontinue other biologic therapies prior to the Baseline Visit to comply with this inclusion criterion must follow the washout periods specified below. If not specified below, biologic therapies must be discontinued at least 5 times the mean terminal elimination half-life of a drug or 3 months prior to Baseline, whichever is longer:
 - ≥ 4 weeks for etanercept;
 - ≥ 8 weeks for adalimumab, infliximab, certolizumab, golimumab, abatacept, tocilizumab, and ixekizumab;

- ≥ 16 weeks for secukinumab;
- ≥ 12 weeks for ustekinumab.
 - No minimum washout prior to Baseline is required for a biologic therapy if an undetectable drug level measured by a commercially available assay is documented.
- 25. Subject must not have had prior exposure for 14 days or more or any prior intolerance to a JAK inhibitor for any indication. The washout period for JAK inhibitors prior to the first dose of study drug is ≥ 30 days or 5 times the half-life, whichever is longer.
- 26. No previous treatment with any cell-depleting therapies including but not limited to anti-CD20 (e.g., rituximab) within 12 months prior to Baseline or until B cell count returns to normal level or pre-treatment level.

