- Subjects who have had an ulcerating reaction to PPD in the past should not be re-exposed and the PPD should be considered positive and do not require subsequent testing with either PPD or QuantiFERON-TB Gold Plus.
- If the QuantiFERON-TB Gold Plus test is indeterminate, then the investigator should perform a local QuantiFERON-TB Gold Plus test (or through the central laboratory if not locally available) to rule out a positive test result. If testing remains indeterminate or is positive, then the subject is considered to be positive for the purpose of this study. If the testing result is negative, then the patient is considered to be negative.
- Interpretation of a positive TB test in low risk subjects: In cases where the QuantiFERON-TB Gold Plus test by the central laboratory is positive and the investigator considers the subject at low risk for TB (i.e., no risk factors identified using the Part I and Part II questions of the TB risk assessment questionnaire at Screening) and has no clinical suspicion of TB, the investigator may perform a local QuantiFERON-TB Gold Plus test (or repeat testing through the central laboratory if not locally available) to confirm the positive test result. If the repeat testing result is negative, the investigator may consider the test to be negative based on his/her clinical judgment; if the repeat testing result is positive or indeterminate, the test is considered positive.
- An equivalent Interferon Gamma Release Assay (IGRA) (such as T-SPOT TB test) may be substituted for the QuantiFERON-TB Gold Plus.
- TB test(s) results will be retained at the site as the original source documentation.

No use or disclosure outside AbbVie is permitted without prior written authorization from AbbVie.

If the subject is experiencing signs or symptoms suspicious for TB or something has changed in the subject's medical history to warrant investigation and a repeat test during the study, the case (including the TB test results) should be discussed with the AbbVie TA MD.

TB Prophylaxis:

Note: Rifampicin and Rifapentine are not allowed for TB prophylaxis while on study drug.

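### Protocol Section 5.4 permits every antibiotic after Week 16, but Section 5.3 and criterion 21 bar strong CYP3A inhibitors and inducers until dosing ends, and rifampicin falls under both rules

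*Protocol*

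**What the plan says.** **The permission.** The antibiotics paragraph of Protocol Section 5.4 allows antibiotics for acute infections during the study and bars them for HS and other chronic inflammatory disorders up to Week 16. It then states: "After Week 16, concomitant use of any antibiotics for any indication, including HS, is permitted". The paragraph has no CYP3A exception and no pointer to Section 5.3.

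**The prohibition.** Section 5.3 has a separate subsection on strong CYP3A inhibitors and inducers. It bars systemic strong inhibitors between Screening and the last dose. For the other class it reads: "use of strong CYP3A inducers is not permitted from 30 days prior to study drug administration through the end of study drug administration". Criterion 21 in Section 5.1 repeats both parts. On inhibitors it reads: "Subject must have no systemic use of known strong cytochrome P450 3A (CYP3A) inhibitors from Screening through the end of study drug administration". Its wording on inducers matches Section 5.3 in both start and end. Table 1 gives examples and places rifampin (rifampicin) in the inducer column.

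**Rifampicin as an HS treatment.** The Synopsis and Section 2.1 list the available treatments for HS, among them "systemic antibiotics (e.g., clindamycin, tetracycline, rifampicin".

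**The Operations Manual.** Under TB prophylaxis in Section 3.19: "Rifampicin and Rifapentine are not allowed for TB prophylaxis while on study drug".

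**The concern.** The Section 5.4 sentence covers all antibiotics and all indications, and it mentions HS expressly. The protocol's own list of HS antibiotics includes a drug that its own table classes as a barred inducer. An investigator treating HS at, say, Week 20 who consults the concomitant-therapy section finds clear permission and nothing that leads to the restriction elsewhere.

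Three things are at stake.

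- **Participant protection.** The sponsor wrote the CYP3A restriction into eligibility and prohibited therapy, and restated it for rifampicin and rifapentine under TB prophylaxis. A general permission should not undercut it by accident, and participants should not be managed differently according to which section a site reads.
- **Consistent classification.** The same prescription is allowed therapy under Section 5.4 and a prohibited concomitant medication under Section 5.3. SAP Appendix A tabulates subjects who took prohibited medication, and Section 5.5 makes introduction of a prohibited drug a ground for stopping study drug where continuing would put the subject at risk. Two sites could record identical use differently.
- **Period 2 data.** Use of a strong inducer or inhibitor could alter upadacitinib exposure at the Week 24 PK sample and during the long-term efficacy and safety follow-up.

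**Working it through.** The plan gives no statistical figure on this point, so the check is a comparison of texts plus the overlap on the visit schedule.

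**1. The rules side by side, for rifampicin given for HS after Week 16**

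| Source | Scope | End of the restriction | Result |
|---|---|---|---|
| Protocol 5.4, antibiotics | All antibiotics, all indications, HS named | Week 16 | Permitted |
| Protocol 5.3, CYP3A subsection, with Table 1 | Strong inducers; rifampicin listed | Last dose | Prohibited |
| Protocol 5.1, criterion 21 | Strong inducers, referring to Table 1 | Last dose | Prohibited |
| Operations Manual 3.19 | Rifampicin and rifapentine for TB prophylaxis | While on study drug | Silent on HS |

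**2. Does other text release the CYP3A bar at Week 16?** No. The Week 16 lead-in in Section 5.3 stands under the background-therapies subheading. The CYP3A rule has its own subheading and its own end point.

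**3. Does other text narrow the permission?** No. Section 5.4 sends interaction questions to the Investigator's Brochure and other questions to the sponsor's medical director. Neither is an exception, and a reader of an unqualified permission has no prompt to ask. The Operations Manual note is limited to TB prophylaxis. No passage says which section prevails.

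**4. Length of the overlap.** From the Activity Schedule, Week 16 is Day 112 and Week 48 is Day 336.

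- 336 − 112 = 224 days; 224 / 7 = 32 weeks.
- 30 mg arm, treated for 48 weeks: 32 / 48 = 67%.
- Placebo arm after its Week 12 switch to 15 mg, treated for 48 − 12 = 36 weeks: 32 / 36 = 89%.

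**5. What falls inside it.** PK samples are scheduled at Baseline and Weeks 2, 8, 12, 16 and 24. Only Week 24 comes after the permission starts. It is one of five on-drug PK visits for the 30 mg arm (Weeks 2, 8, 12, 16, 24) and one of two for the 15 mg group (Weeks 16, 24). The Week 12 primary and secondary endpoints precede the window. Period 2 efficacy and safety data after Week 16 lie within it.

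**The case against.** The best counter-argument is that the passages can be read together. The Section 5.4 paragraph is organised by indication and time. Its Week 16 sentence mirrors Section 5.3 item 5, which bars antibiotics for HS until after the Week 16 assessments. Its opening sentence allows antibiotics for acute infection throughout the study, also without a CYP3A exception, which suggests that the paragraph was never meant to deal with interactions. The CYP3A rule is the more specific one, and the TB text agrees with it. This is a plausible account of intent. However, the protocol states no precedence rule, and the permission is itself specific about HS, so the ambiguity remains.

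A reader might also draw stronger conclusions that the documents do not support:

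- **That a site must break one section or the other.** Section 5.4 permits and does not require. A site that withholds rifampicin breaches nothing in it. Only reliance on the permission produces a breach.
- **That every antibacterial in Table 1 is on both sides by the protocol's own words.** Only rifampicin is named both as an HS antibiotic and as a barred drug. Classing other Table 1 entries as antibacterials draws on general knowledge. The inhibitor bar also covers systemic use only.
- **That Section 5.3 item 1 is a second contradiction.** Item 1 begins "Throughout the study, any other systemic therapy that can also be used to treat HS", but its examples are corticosteroids and immunosuppressants, and antibiotics have their own item 5 in the same list. The wording could be clearer, but the conflict is weak.
- **That the PK analysis leaves such use unhandled.** SAP Section 1.0 places PK analyses outside its scope, so its silence proves nothing.

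**Conclusion.** The contradiction is real and rests on the protocol's own text. For rifampicin used for HS after Week 16, one section permits what two others prohibit, and nothing in the documents settles which governs. A site acting on Section 5.4 would break the CYP3A restriction, and its patient would count under SAP Appendix A as having taken a prohibited medication.

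The size is limited. The 67% and 89% figures say how long both rules are in force together. They do not measure use, altered exposure or bias. The documents give neither the strength of the interaction nor the expected frequency of such prescriptions, so effects on safety, the Week 24 PK sample and Period 2 results are possible but not shown. Period 2 efficacy is only summarised as observed cases, and SAP Section 9.2.3 already drops efficacy values after antibiotics for HS-related infections. The primary and secondary analyses at Week 12 are untouched.

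This is therefore a wording conflict in a participant-protection rule. It deserves correction because it is clear and cheap to fix, but it does not threaten the trial's main result.

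A reader might go further and ask for excluded PK records, adverse-event rates with and without the affected time, or a 30-day flag after inducer use. The documents do not make these necessary. The 30 days in Section 5.3 and criterion 21 is a restriction before dosing and is not stated as a clearance period after use on study.

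**What to change.** Reconcile the Week 16 sentence in Section 5.4 with the CYP3A subsection of Section 5.3, criterion 21 and Table 1, so that a single rule applies after Week 16 to antibiotics that are strong CYP3A inhibitors or inducers. Put a cross-reference to that rule at the Section 5.4 sentence. Which rule stands is a decision for the sponsor's medical team.

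In the same edit the sponsor may clarify how Section 5.3 item 1 relates to item 5 on antibiotics.

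The cost is one sentence and a cross-reference, by amendment or site memo. No new data are needed, because Section 5.4 already requires concomitant medications to be recorded with reason and dates. The sample size and the planned efficacy analyses do not change.
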